**Determination of FIX recovery (and TGA parameters, if applicable)**

- a) Pre-infusion blood draw for FIX activity (and TGA parameters, if applicable) within 0.5 h of start of infusion
- b) Infusion of BAX326, at dose of  $75 \pm 5$  IU/kg at a rate not to exceed 10 mL/min
- c) Post-infusion blood draw for FIX activity (and TGA parameters, if applicable) at  $30 \pm 5$  minutes
- d) Vital signs at  $30 \pm 5$  minutes and 2 h ± 10 minutes following completion of the infusion
- Hand out subject diary
- Dispense IP supplies for a maximum of 2 months

Throughout: AEs and concomitant medication and non-drug therapy use.

**Table 21.1-1**  
**Flow Diagram of Required Procedures for Baxalta Clinical Study 251001**

**4b. Study Visit Week 4 ± 1 in Subjects Transitioning from BAX326 Pivotal or BAX326 Pediatric Study**

This visit should occur upon availability of the laboratory results within 4 ±1 weeks following screening. For subjects switching back to this study from the surgery studyxxiii, the respective visit window may be extended from ± 1 week to ± 2 weeks.

At this study visit the following procedures will be carried out:

- 1) Review and discuss subject diary
- 2) Record AEs
- 3) Concomitant medication and non-drug therapy use
- 4) Hand out subject diary
- 5) Dispense IP supplies for 2 months

Throughout: AEs and concomitant medication and non-drug therapy use.

**5. PK-Tailored Dosing:**

**5a. Start of PK tailored treatment regimen**

Subjects will be contacted by the investigator regarding the dose and treatment regimen of the PK tailored regimen upon availability of PK results. Subjects to start PK tailored treatment regimen 4±1 weeks prior to the next 3 monthly visit

**5b. Phone Calls by Study Site to Subjects**

Phone calls from study sites to subjects have to occur at:

- 8 weeks ± 1 week
- 17 weeks ± 1 week and
- 22 weeks ± 1 week following the first PK-tailored dose at study site.

The following information is to be requested by the site and entered into eCRF:

- Occurrence of bleeding episodes, exact location and cause
- Occurrence of AEs

xxiii Surgery Study 251002 was completed in May 2014. Thirty unique subjects underwent 38 surgeries.

**Table 21.1-1**  
**Flow Diagram of Required Procedures for Baxalta Clinical Study 251001**

**APPLICABLE TO ALL PROPHYLACTIC REGIMENS THROUGHOUT**  
**THE STUDY:**

Dose and/or frequency adjustments should be performed if a subject meets either of the following criteria:

- **Two or more spontaneous** (not related to trauma) bleeding episodes in the same target joint within any 3-month period, **OR**
- **One or more spontaneous** (not related to trauma) bleeding episodes in a non-target joint or a non-joint within any 3-month period

In such a case, the dose and/or frequency will be increased. It is recommended to consult the sponsor.

**In subjects with severe hemophilic arthropathy and/or target joints who continue experiencing recurrent bleeding episodes despite adjustments of the prophylactic dose and/or dosing frequency, an ultrasound of the affected joint(s) should be performed to verify the presence of a bleed.**

**Table 21.1-1**  
**Flow Diagram of Required Procedures for Baxalta Clinical Study 251001**

**6. Study Visits Every 3 Months ± 1 Week Following Screening in Subjects Transitioning from BAX326 Pivotal or BAX326 Pediatric Study; Study Visits Every 3 Months ± 1 Week Following ED1 for Newly Recruited Subjects**

Each visit must be arranged so that there is a wash-out period of at least 5 days (120 hours), preferably 7 days, from the latest dose of BAX326. The subject must not be actively bleeding. For subjects switching back to this study from the surgery studyxxiv, the respective visit window may be extended from ± 1 week to ± 2 weeks.

At each study visit the following procedures will be carried out:

Prior to the recovery assessment:

- Review and discuss subject diary
- Review and discuss the number of spontaneous bleeding episodes
- Review number of EDs to BAX326
- Record AEs
- Concomitant medication and non-drug therapy use
- HR QoL including Patient Activity Level pre- or post-infusion of BAX326 – every second visit (every 6 months ±1 week)
- Collection of Health Resource Utilization items
- Physical examination
- Occurrence of target joints
- Blood draws for:
  - a) Immunology (pre-infusion of IP)
  - b) Hematology and clinical chemistry
- Urine sample for urinalysis
- Vital signs within 15 minutes of start of infusion
- CD4 count will be assessed **once a year**.
- **Assessment of FIX Recovery (and TGA parameters, if applicable)**
  - a) Pre-infusion blood draw for FIX activity (and TGA parameters, if applicable) within 0.5 h of start of infusion
  - b) Infusion of  $75 \pm 5$  IU/kg BAX326 at a rate not to exceed 10 mL/min
  - c) Post-infusion blood draw for FIX activity (and TGA parameters, if applicable) at  $30 \pm 5$  minutes
  - d) Vital signs at  $30 \pm 5$  minutes and  $2 h \pm 10$  minutes following completion of the infusion

xxiv Surgery Study 251002 was completed in May 2014. Thirty unique subjects underwent 38 surgeries.

**Table 21.1-1**  
**Flow Diagram of Required Procedures for Baxalta Clinical Study 251001**

In all subjects receiving modified or PK-tailored prophylactic treatment (or approximately 20 subjects) and in a subset of approximately 20 subjects on twice-weekly standard with BAX326, TGA testing concurrent with IR determination will be performed at 3 regular 3-month visits.

- Hand out subject diary
- Dispense IP supplies for a maximum of 3 months

**7. Determination of TGA Parameters and Additional Pre- and Post-Infusion FIX Levels in Standard Cohort Receiving Twice-Weekly Prophylactic Infusions of BAX326**

In a subgroup of up to 20 subjects  $\geq$  12 years of age receiving twice-weekly prophylactic infusions of BAX326, blood samples for determination of TGA parameters concurrent with pre- and post-infusion FIX determination will be performed **during a 6-month period** at the following time points **after having obtained Informed Consent**:

**At regular 3-month study visit:**

- Initially, ie, at start of the 6-month period
- after 3 months  $\pm$  1 week and
- after 6 months  $\pm$  1 week of twice-weekly prophylactic infusions

According to the requirements of the 3-month study visits, there will be a wash-out period of at least 5 days (120 h), preferably 7 days. Concurrent with the determination of FIX recovery, pre- and post-infusion blood samples for TGA parameters are also drawn.

FIX activity and TGA parameters will also be determined prior to and following a regular prophylactic infusion at 4 additional time points in a 6-month period, **without the requirement of a wash-out period**:

- On 2 occasions, these should be assessed 3 days after a prophylactic infusion, ie, before and after the subsequent prophylactic infusion of BAX326:
  - Last prophylactic infusion approximately 72 hours (3 days) prior to FIX and TGA determination
  - Within 30 minutes prior to regular prophylactic infusion blood sampling for FIX activity and TGA parameters
  - Administration of regular prophylactic infusion of BAX326
  - 30 $\pm$ 5 minutes post-infusion blood sampling for FIX activity and TGA parameters
- On another 2 occasions, these should be assessed 4 days after a prophylactic infusion, ie, before and after the subsequent prophylactic infusion of BAX326:
  - Last prophylactic infusion approximately 96 hours (4 days) prior to FIX and TGA determination
  - Within 30 minutes prior to regular prophylactic infusion blood sampling for FIX activity and TGA parameters
  - Administration of regular prophylactic infusion of BAX326
  - 30 $\pm$ 5 minutes post-infusion blood sampling for FIX activity and TGA parameters

**Table 21.1-1**  
**Flow Diagram of Required Procedures for Baxalta Clinical Study 251001**

**8. Study Completion/Termination Visit**

If the subject has accumulated a total of 100 EDs during the course of Studies 250901/251101 and 251001, or BAX326 is licensed in the subject's country, whichever occurs last, this will be the subject's study completion/ termination visit.

The visit must be arranged so that there is a wash-out period of at least 5 days (120 hours), preferably 7 days, from the previous dose of BAX326 and the subject must not be actively bleeding.

Prior to the recovery assessment:

- 1) Review and discuss subject diary
- 2) Record AEs
- 3) Concomitant medication and non-drug therapy use
- 4) Occurrence of target joints
- 5) Collect Health Resource Utilization items
- 6) Physical examination
- 7) Blood draws for:
  - a) Immunology (pre-infusion of IP)
  - b) Hematology and clinical chemistry
- 8) Urine sample for urinalysis
- 9) Assess HR QoL items pre- or post-infusion of BAX326 including Patient Activity Level
- 10) Vital signs within 15 minutes of start of infusion

**11) Assessment of FIX recovery (and determination of TGA parameters, if applicable)**

- a) Pre-infusion blood draw for FIX activity (and TGA parameters, if applicable) within 0.5 h of start of infusion
- b) Infusion of  $75 \pm 5$  IU/kg BAX326
- c) Post-infusion blood draw for FIX activity (and TGA parameters, if applicable) at  $30 \pm 5$  minutes
- d) Vital signs at  $30 \pm 5$  minutes and 2 h  $\pm 10$  minutes following completion of the infusion

## 21.2 Schedule of Study Procedures and Assessments

### 21.2.1 Schedule of Study Procedures and Assessments for Subjects Transitioning from 250901 or 251101

**Table 21.2-1**  
**Schedule of Study Procedures and Assessments for Subjects Transitioning from 250901 or 251101**

Procedures/Assessments	Screening Visit	Study Visit Week 4 ± 1 j,k	Study Visits: Every 3 Months ± 1 Week j	Study Completion / Termination Visit l
Informed consent a	X			
Eligibility criteria r	X	X	X r	
Medical history	X b			
Medications and non-drug therapies	X b	X	X	X
Physical examination c	X b		X	X
Occurrence of target joints n	X		X h	X
Adverse events	X b	X	X	X
Laboratories d	X b	X m	X	X
PK study p			X p	
Vital signs e	X	X m	X	X
Dispense IP f	X g	X o	X	
Incremental Recovery	X	X m	X	X
Hand out subject diary	X	X	X	
Review subject diary		X	X	X
Re-evaluation of prophylactic regimen q		X q	X q	X
HR QoL incl Patient Activity Level i			X	X
Health Resource Use			X	X

*Continued on next page*

*Continued*

- a Informed consent must be obtained before starting any other procedure related to the continuation study.
- b Data to be transcribed from 250901/251101 study completion/termination visit to the screening visit of the continuation study (except for CD4 count, which must be assessed to confirm subject's eligibility).
- c Includes height and weight at screening and weight at the pre-infusion assessments.
- d For laboratory assessments, see [Table 21.3-1](#). At all assessments, subjects must not be actively bleeding.
- e Pulse, respiration, supine blood pressure, and temperature to be assessed within 15 minutes prior to the start of infusion and  $30 \pm 5$  minutes and 2 h  $\pm 10$  minutes following infusion.
- f The treatment with BAX326 will be either a prophylactic treatment twice weekly with 50 IU/kg, OR a modified prophylaxis determined by the investigator, OR a PK-tailored prophylactic administration, OR on-demand treatment.
- g The Investigational Product at screening visit should be dispensed for the period of 4 weeks  $\pm 1$  week.
- h In transitioning subjects occurrence of target joints will be evaluated and documented every 3 months.
- i HR QoL will be assessed at every second visit.
- j For subjects switching back to this continuation study from the surgery studyxxv, the respective visit window may be extended from  $\pm 1$  week to  $\pm 2$  weeks. Every 3 month visits are calculated from Screening for transitioning subjects.
- k For subjects receiving a PK-tailored treatment regimen, the study site will call the subjects at  $8 \pm 1$ ,  $17 \pm 1$  and  $22 \pm 1$  weeks after start of treatment to discuss the potential occurrence of bleeding episodes and/or AEs.
- l Study completion/ termination visit should be performed when BAX326 is licensed in the respective country, or the subject has accumulated approximately 100 EDs to BAX326, whichever occurs last.
- m Only subjects receiving PK-tailored treatment: After  $4 \pm 1$  weeks of start of treatment with a PK tailored treatment regimen. These subjects have two Week  $4 \pm 1$  visits: first visit = regular visit to confirm eligibility; second visit = visit for PK-tailored subset after 4 weeks of start of PK-tailored treatment regimen and 2 months prior to next scheduled 3-month visit.
- n A target joint is defined as one in which there have been  $\geq 4$  bleeds in the 6 months prior to study entry or during the last 6-month period being in the study.
- o Dispense IP supplies for 2 months
- p Abbreviated PK study will be performed in subjects planned to receive a PK-tailored treatment regimen and who have not participated in a PK study with BAX326 in either BAX326 Pivotal or BAX326 Surgery. It should take place at one of the 3-month study visits.
- q In subjects receiving a prophylactic treatment (standard, modified or PK-tailored) the regimen needs to be re-evaluated and if needed adjusted. Further guidance is provided under protocol Section [8.6.3.1](#).
- r Only CD4 count needs to be assessed every 12 months to confirm subject's eligibility.

---

xxv Surgery Study 251002 was completed in May 2014. Thirty unique subjects underwent 38 surgeries.

## 21.2.2 Schedule of Study Procedures and Assessments for Newly Recruited Subjects

**Table 21.2-2**  
**Schedule of Study Procedures and Assessments for Newly Recruited Subjects**

Procedures/Assessments	Screening Visit	First Infusion (ED1)	Study Visit Week 4 ± 1 ij	Study Visits: Every 3 Months ± 1 Week i	Study Completion / Termination Visit k
Informed consent a	X				
Eligibility criteria o	X			X o	
Medical history	X				
Medications and non-drug therapies	X	X	X	X	X
Physical examination c	X	X	X	X	X
Occurrence of target joints l	X			X	X
Adverse events		X	X	X	X
Laboratories d	X	X	X	X	X
PK Study b		X b			
Vital signs e	X	X	X	X	X
Dispense IP f		X g	X n	X	
Incremental Recovery	X	X	X	X	X
Hand out subject diary	X	X	X	X	
Review subject diary		X	X	X	X
Re-evaluation of prophylactic regimen m			X	X m	X m
HR QoL h	X	X		X	X
Health Resource Use	X	X	X	X	X

*Continued on Next Page*

*Continued*

- a Informed consent must be obtained before starting any other procedure related to the continuation study.
- b Abbreviated PK study will be performed in those subjects who are planned to receive a PK-tailored dosing regimen. Please refer to [Table 21.5-1](#) for further details on PK assessment.
- c Includes height and weight at screening and weight at the pre-infusion assessments.
- d For laboratory assessments, see [Table 21.4-1](#). At all assessments, subjects must not be actively bleeding.
- e Pulse, respiration, supine blood pressure, and temperature to be assessed within 15 minutes prior to the start of infusion and  $30 \pm 5$  minutes and  $2 \text{ h} \pm 10$  minutes following infusion.
- f The treatment with BAX326 will be either a prophylactic treatment twice weekly with 50 IU/kg, OR a modified prophylaxis determined by the investigator, OR a PK-tailored prophylactic treatment regimen.
- g The Investigational Product at ED1 visit should be dispensed for the period of  $4 \text{ weeks} \pm 1$  week.
- h HR QoL including Patient Activity Level will be assessed at every second visit.
- i For subjects switching back to this continuation study from the surgery studyxxvi, the respective visit window may be extended from  $\pm 1$  week to  $\pm 2$  weeks.
- j For subjects receiving a PK-tailored treatment regimen, the study site will call the subjects at  $8 \pm 1$ ,  $17 \pm 1$  and  $22 \pm 1$  weeks after start of treatment to discuss the potential occurrence of bleeding episodes and/or AEs. Every 3 month visits are calculated from the ED1 visit for newly recruited subjects.
- k Study completion/ termination visit should be performed when BAX326 is licensed in the respective country, or the subject has accumulated a total of 100 EDs to BAX326, whichever occurs last.
- l A target joint is defined as one in which there have been  $\geq 4$  bleeds in the 6 months prior to study entry or during the last 6-month period being in the study.
- m In subjects receiving a prophylactic treatment (standard, modified or PK-tailored) the regimen needs to be re-evaluated and if needed adjusted. Further guidance is provided under protocol Section [8.6.3.1](#).
- n Dispense IP supplies for 2 months
- o Only CD4 count needs to be assessed every 12 months to confirm subject's eligibility.

---

xxvi Surgery Study 251002 was completed in May 2014. Thirty unique subjects underwent 38 surgeries.

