### **8.1.2 Newly Recruited Subjects**

At least 25 subjects who have not previously been exposed to BAX326 will be enrolled (Cohort 2). Once eligibility criteria are confirmed, subjects will receive prophylactic treatment over a period of up to approximately 100 EDs to BAX326, or until BAX326 is approved in the subject's country, whichever occurs last, but no later than December 31, 2016. A limited number of patients may not have reached 100 EDs by that date and they will continue until they have reached approximately 100 EDs.

---

xiii 1 month calculated on a 30-day basis

The treatment regimen with BAX326 will be at the discretion of the investigator and will consist of one of the following treatment options:

- Standard prophylaxis with twice weekly prophylactic infusions of 50 IU/kg (range of 40-60 IU/kg, which may be increased to 75 IU/kg, in subjects  $\geq$  12 years of age; range of 40-80 IU/kg in pediatric subjects  $<$  12 years), or
- modified prophylaxis determined by the investigator. The dose can be increased up to 100 IU/kg, if applicable; or
- PK-tailored prophylaxis. The maximum dose is 120 IU/kg.

Hemostatic efficacy, safety, and immunogenicity assessments will be performed at Week  $4 \pm 1$ , Month  $3 \pm 1$  week and thereafter every 3 months  $\pm 1$  week (see Section 8.1.1). IR will be determined at the same time points. An additional inhibitor test will be performed immediately before the first exposure to BAX326, as well as an IR during the first infusion of BAX326. The subject will be monitored for vital signs and the occurrence of AEs. Subjects receiving PK-tailored prophylaxis will follow the schedule as described in Section 8.1.3.

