### **11.1.3 Determination of Incremental Recovery Over Time in Newly Recruited Subjects and Subjects Receiving a PK-Tailored Dose**

FIX levels to determine IR will be assessed at the following visits:

- At ED1 (only newly recruited subjects)xxi
- At Week 4 ± 1
- At Month 3 ± 1 week
- Every three months ± 1 week
- At study termination/completion

---

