#### **14.3.2.2 Pharmacokinetics**

PK parameters will be calculated for all subjects planned to receive a PK-tailored treatment regimen using a non-linear mixed effects model approach.

The available PK data (FIX activity levels) from pivotal study 250901, pediatric study 251101 and surgery study 251002 will be utilized together in the model and strengthen the estimation of the full PK curve even if only sparse samples are available for an individual.

The following PK parameters for FIX will be reported using descriptive statistics: AUC0-∞ (area under the plasma concentration/time curve from time 0 to infinity), IR, T1/2 (elimination phase half-life), MRT (mean residence time), CL (clearance), Vss (Volume of distribution at steady state). Incremental recovery (IR) will be determined as the changes in FIX activity level from pre-infusion to 30 ± 5 minute post-infusion, divided by dose, and reported as (IU/dL)/(IU/kg). FIX activity levels at pre-infusion reported as < 1% will be used as 0.5% for the calculation of IR.

Incremental recovery of FIX will be summarized by visit and displayed graphically over time for each subject. Also the change from baseline (at screening visit) will be described using summary statistics. As the maximum dose can be 120 IU/kg any doses higher than 120 IU/kg are not allowed and therefore frequencies requiring a higher are excluded.

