**Table 21.1-1**  
**Flow Diagram of Required Procedures for Baxalta Clinical Study 251001**

**3. First Infusion in Newly Recruited Subjects (ED1)**

Once eligibility criteria are confirmed, the subject will receive the first infusion at the study site which will include an assessment of IR. For subjects planned to receive a PK-tailored dose regimen, please see procedures described for assessment of PK.

At least 5 days (120 hours), preferably 7 days, must have elapsed since the previous FIX administration and the subject must not be actively bleeding.

Procedures to be done **before the infusion**:

- 1) Review and discuss subject diary
- 2) Record AEs
- 3) Concomitant medication and non-drug therapy
- 4) Physical examination including weight
- 5) Assess HR QoL including Patient Activity Level and collect Health Resource Utilization items pre- or post-infusion of BAX326
- 6) Vital signs within 15 minutes of start of infusion

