## 21.4 Clinical Laboratory Assessments for Newly Recruited Subjects

**Table 21.4-1**  
**Clinical Laboratory Assessments for Newly Recruited Subjectsa**

Assessments	Screening Visit	First Infusion (ED1)	Study Visit 4 ± 1 Week	StudyVisits: Every 3 Months ± 1 Week j	Study Completion/ Termination Visit d
CD4 count	X			X i	
HIV test and viral load, if positive	X				X
Genetics and HLA-genotype	X o				
Pregnancy Test (if applicable) m	X			X	X
FIX activity	X				
FIX antigen	X				
FIX recovery b		X	X k	X	X
Abbreviated PK k		(X)	(X)	(X)	
Hematology c	X		X	X	X
Clinical Chemistry d	X		X	X	X
Urinalysis e	X		X	X	X
Immunology f	X	X g	X h	X h	X h
Hepatitis serology	X				
INR	X				
TGA l		X	X	X	X
Prothrombotic markers n	X				

*Continued on Next Page*

*Continued*

- a At all assessments, subjects must not be actively bleeding. In addition to the assessments shown, clinical laboratory assessments should be performed whenever clinically indicated.
- b For assessment of recovery: samples will be taken within 0.5 h before the start of the infusion, and at 0.5 h  $\pm$  5 minutes after the infusion. The washout period of at least 5 days (120 h), preferably 7 days, is necessary.
- c Hematology assessments include: hemoglobin, hematocrit, red blood cell count, and white blood cell count with differential (ie, basophils, eosinophils, lymphocytes, monocytes, neutrophils), mean corpuscular volume (MCV), mean corpuscular hemoglobin concentration (MCHC), and platelet count.
- d Clinical chemistry assessments include: sodium, potassium, chloride, bicarbonate, total protein, albumin, alanine aminotransferase (ALT), aspartate aminotransferase (AST), total bilirubin, alkaline phosphatase, blood urea nitrogen (BUN), creatinine, and glucose.
- e Urinalysis assessment: protein. Urinalysis should also be performed if inhibitors are detected.

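### Table 21.2-2 marks Incremental Recovery, which needs a BAX326 infusion, at Screening for newly recruited subjects, whereas Sections 8.1.2 and 11.1.3 and Table 21.1-1 place the first infusion and first IR at ED1, after eligibility

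*Protocol*

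**What the plan says.** Protocol Table 21.2-2, the visit schedule for Cohort 2, has the row "Incremental Recovery X X X X X". Its five columns are Screening, First Infusion (ED1), Week 4, the three-monthly visits and Completion/Termination. No footnote restricts the Screening mark.

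Section 14.3.2.2 defines the measurement: "Incremental recovery (IR) will be determined as the changes in FIX activity level from pre-infusion to" a sample 30 ± 5 minutes after infusion, divided by dose. Footnote b of Table 21.4-1 says that "samples will be taken within 0.5 h before the start of the infusion", with a second sample afterwards. Section 11.1 sets the dose for IR at regular visits at 75 ± 5 IU/kg.

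Elsewhere the timing for Cohort 2 differs:

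- Section 8.1.2: "Once eligibility criteria are confirmed, subjects will receive prophylactic treatment over a period of up to approximately 100 EDs to BAX326". It also states "An additional inhibitor test will be performed immediately before the first exposure to BAX326", "as well as an IR during the first infusion of BAX326".
- Section 11.1.3: the list of IR visits opens with "At ED1 (only newly recruited subjects" and contains no screening entry.
- Table 21.1-1 item 3: "Once eligibility criteria are confirmed, the subject will receive the first infusion at the study site which will include an assessment of IR".
- Table 21.1-1 item 1b: the numbered screening steps include a FIX activity draw and end with the eligibility assessment. No infusion is listed.
- Table 21.4-1: FIX recovery is blank at Screening and first marked at ED1.

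**The concern.** Section 10.3 refers sites, by title, to the Schedule of Study Procedures and Assessments for what is done at each visit, screening included. Table 21.2-2 is therefore an operative instruction, and it disagrees with the narrative on when a subject first receives the product.

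Four things are at stake if the cell is followed.

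1. **Exposure before eligibility.** Central-laboratory results on which eligibility depends, such as FIX level, inhibitor titer and CD4 count, would be pending at the time of infusion. Section 6.2 notes that inhibitor onset may be complicated by anaphylaxis on re-exposure to FIX.
2. **The ED1 inhibitor sample.** It is meant to be taken just before first exposure. It would become a post-exposure sample.
3. **The analysis set.** The Full Analysis Set (FAS; Protocol 14.2, SAP 4.1) takes in anyone exposed to any amount of product. Screen failures infused at screening would enter it, and SAP 8 uses it for all safety endpoints, including the primary outcome.
4. **The IR baseline.** The protocol synopsis and Section 14.3.2.2 put it at the screening visit without separating cohorts. The visit conflict therefore carries through to the change-from-baseline summary in SAP 9.1.

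**Working it through.** No sample-size or power figure is involved. The check sets the passages side by side.

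**Step 1. Does an IR mark imply an infusion?** SAP 9.1 gives IR = (C at 30 min − C pre-infusion) / (dose per kg). With no dose there is neither a numerator nor a denominator. A mark for IR is a mark for an infusion. At 75 ± 5 IU/kg this means 75 − 5 = 70 to 75 + 5 = 80 IU/kg.

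**Step 2. Could the mark be a text-extraction slip?** The row has five marks for five columns. A column shift cannot produce a full row, so the Screening mark belongs to the table.

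**Step 3. What does each place say about infusion or IR at Screening in Cohort 2?**

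| Place in the protocol | Infusion or IR at Screening? |
|---|---|
| Table 21.2-2, IR row | Yes |
| Table 21.2-2, heading of the next column | No: ED1 is named as the first infusion |
| Section 8.1.2 | No: treatment follows eligibility, first IR at first infusion |
| Section 11.1.3 | No: list starts at ED1 |
| Table 21.1-1 item 1b | None listed |
| Table 21.1-1 item 3 | No: first infusion with IR once eligible |
| Table 21.4-1, FIX recovery row | Blank |

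One cell says yes. Six other places, one of them in the same table, say no or show nothing. The abbreviated PK infusion also waits for confirmed eligibility (Table 21.4-1 footnote k; Table 21.5-1 footnote b).

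**Step 4. Does anything lend weight to the literal reading?** Three things do.

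- The IR baseline text puts baseline at screening for both cohorts.
- Footnote e, attached to a vital-signs row that is marked at Screening, times the readings only around an infusion.
- Item 1b requires the same washout at screening (at least 5 days) as Table 21.4-1 requires for a recovery test, so nothing practical would stop a site.

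**Step 5. Is the Cohort 2 IR baseline defined?** If the first IR is at ED1, there is no screening IR, and the protocol's baseline visit has no value. SAP 5.3 takes the most recent value before the first infusion. By Step 1, a BAX326-naive subject has no IR before a first infusion. Neither definition yields a value, yet SAP 9.1 summarises IR change from baseline to end of study, and SAP 5.5 justifies that comparison as showing whether antibodies have affected recovery.

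**Step 6. How many subjects, and for how long?** The schedule covers at least 25 newly recruited subjects plus all who fail screening; the documents do not give the number of failures. Screening evaluations must be completed within 42 days (Section 10.3.2), so exposure could precede a settled eligibility decision by up to about that long.

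**The case against.** The strongest reply is that the table cannot be followed literally as a whole. An infusion at Screening would falsify the heading of its next column, and its Adverse events row is blank at Screening. Footnote d sends sites to Table 21.4-1 for laboratory work, where recovery is blank and only a FIX activity level is due at Screening. Item 1b walks through screening with no infusion. All of this stands. A reader might infer that the protocol instructs sites to dose unscreened subjects; the documents do not support that. They support only that a site relying on this cell could infuse before eligibility is confirmed.

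The safety consequence is also narrower than the word naive suggests. These subjects are naive to BAX326, not to FIX: they need at least 150 prior exposure days, or 50 if under 6 years. Medical history is taken at screening, and a history of inhibitors or of allergy to FIX concentrate excludes them. Only the criteria awaiting laboratory results would be unchecked. Immunology is also sampled at screening, so an inhibitor result from before exposure could still exist if that draw came first. This stands too, and limits the loss to the ED1 sample.

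Footnote e can be read as applying only where an infusion takes place, since item 1b lists screening vital signs without infusion timing. That is reasonable, but the footnote does not say so.

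Two further inferences should not be drawn. The blank Dispense IP cell at Screening proves nothing either way: the same cell is blank at Termination, where an IR infusion is given. Nor do the documents say that the row was carried over from Table 21.2-1. The same mark fits Cohort 1, whose members are already on BAX326, but that does not explain how it came to be in Table 21.2-2.

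**Conclusion.** The inconsistency is real and should be corrected. It is an internal contradiction, not a design choice. One unfootnoted cell places an IR infusion at Screening; Sections 8.1.2 and 11.1.3, Table 21.1-1 items 1b and 3, Table 21.4-1 and the table's own ED1 heading do not.

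The practical risk is conditional on a site acting on that cell. In that event a FIX-treated subject new to BAX326 could receive 70 to 80 IU/kg with eligibility results pending, the ED1 inhibitor sample would follow first exposure, and infused screen failures would join the FAS. The documents give no evidence that any site did this, and the surrounding text makes it less likely.

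The baseline gap does not depend on site behaviour. If the first IR is at ED1, as the other passages have it, neither the protocol nor the SAP defines an IR baseline for Cohort 2.

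**What to change.** 1. In Table 21.2-2, reconcile the Screening cell of the IR row with Sections 8.1.2 and 11.1.3, Table 21.1-1 items 1b and 3, and Table 21.4-1, so that all give the same visit for the first IR in Cohort 2. Which visit that is, is for the sponsor to state.
2. Reconcile footnote e in the same change, so that its infusion-linked timing is tied to visits at which an infusion is scheduled.
3. Reconcile the IR baseline text in the synopsis, Protocol 14.3.2.2 and SAP 5.3, and name the IR measurement that serves as the Cohort 2 baseline in SAP 9.1.

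The cost is one table cell, one footnote and a sentence or two of baseline text, through an amendment or a clarification letter to sites together with a SAP edit. No data are lost. If subjects have already been screened under this table, comparing infusion dates with eligibility dates in Cohort 2 would show whether the cell was ever acted on, and the result should be reported with the FAS.
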